**PROTOCOL SUMMARY**

Sponsor	The University of Washington
Protocol Title	Branched Thoracic Endovascular Grafts for the Treatment of Thoraco-abdominal Aortic Aneurysms (B-TEVAR)
Study Description	
An investigator-initiated, prospective, consecutively enrolling, non-randomized single institution clinical evaluation of the safety and effectiveness of either: 1) physician modification of a currently FDA- approved off the shelf thoracic aortic stent graft (COOK Zenith® TX2®); or
 
2) Thoracoabdominal Custom Branch/Fenestrated Endovascular Stent-Graft (Cook Medical); or 3) Cook t-Branch Endovascular Stent Graft or 4) Cook Low Profile (LP) t-Branch or Custom Made Device (CMD) to preserve branch vessels when used in the treatment of patients with thoraco-abdominal aortic aneurysms.

Study Objectives	
The primary objectives of this study are to determine whether physician modified branched endovascular grafts are a safe and effective method of treating patients with thoraco-abdominal aortic aneurysms.
 
The safety of physician modified endovascular grafts will be determined by evaluating the proportion of patients that experience a rate of Major Adverse Events.
 
The effectiveness of physician modified endovascular grafts will be determined by evaluating the proportion of patients that achieve Treatment Success at 12 months post-procedure.

Study Primary Endpoints	
The primary safety endpoint is defined as the proportion of subjects who experience a Major Adverse Event within 30 days of the B-TEVAR procedure.
 
The primary effectiveness endpoint is the proportion of subjects that achieve Treatment Success. Treatment Success is a composite endpoint assessed at 12 months following implantation of the B-TEVAR device that requires the following criteria to be met:
 
 
• Technical Success, defined as successful delivery and deployment of the physician modified graft with preservation of unimpeded flow to those branch vessels intended to be preserved.
 
• Freedom from Type I & III endoleaks
 
• Freedom from stent graft migration
 
• Freedom from aortic aneurysm enlargement
 
• Freedom from aortic aneurysm rupture
 
• Freedom from conversion to open repair
 

Study Secondary Endpoints	
The following secondary safety endpoints will be evaluated at 30 days, 12 months and annually to 5 years after implantation of the B-TEVAR device:
 
 
• Mortality rates
 
• Aneurysm related mortality
 
• Major Adverse Events (MAE)
 
• Conversion to open repair
 
• Aneurysm rupture
 
 
The following secondary effectiveness endpoints will be evaluated at 30 days, 12 months and annually to 5 years after implantation of the B-TEVAR device:
 
 
• Technical Success
 
• Freedom from Type I & III endoleaks
 
• Freedom from stent graft migration
 
• Freedom from aortic aneurysm enlargement
 
• Freedom from aneurysm rupture
 

	
 
• Freedom from conversion to open repair
 
• Radiographic evidence of device integrity
 
• Freedom from thromboembolic events
 
• Freedom from re-intervention
 

Clinical Utility Measurements	
The following Clinical Utility Measurements will be evaluated:
 
 
• Conduit usage
 
• Blood loss
 
• ICU stay
 
• Length of hospital stay
 
• Type of anesthesia
 
• Secondary interventions
 

Patient Population	
The total Treatment Group includes 60 patients, including those who are planning to undergo single or two-staged approach to repair.

Follow-Up Intervals	
Treatment Group follow up intervals will consist of 1, 6, and 12 months following the B-TEVAR implant procedure, then annually through 5 years.

Follow- Up Events	
Treatment Group follow up:
 
 
• Physical exam
 
• Contrast Enhanced Spiral Chest/Abdominal/Pelvic CT
 
• Device/aneurysm assessment based on imaging
 
• Laboratory Assessment
 
• Assessment of Adverse Events
 
• Assessment of concomitant medications (only anticoagulants, anti-platelets, antibiotics, statins, Beta blockers and ACE inhibitors/ARB)
 

Investigational Sites	
The University of Washington (University of Washington Medical Center and Harborview Medical Center) will be the only site involved in this trial.

Anatomic Criteria	
Adequate proximal and distal seal and fixation sites:
 
A. Non-aneurysmal proximal aortic seal zone:
 
 
1. with a length of 25 mm of proximal seal in non-aneurysmal aorta, with or without coverage of the left subclavian artery,
 
2. with an outer wall diameter of no less than 15 mm and no greater than 42 mm, and
 
 
B. Non-aneurysmal distal aortic or iliac landing zone:
 
 
3. With a length of at least 15 mm,
 
4. Aortic seal zone no less than 15 mm and no greater than 42 mm or
 
5. Iliac seal zone with an outer wall diameter of no less than 8 mm and no greater than 23 mm.
 
 
No greater than 5 visceral vessels <math>\geq</math> 4 mm in diameter requiring revascularization
 
Femoral/Iliac arterial access to allow introduction of the device into the aorta with or without the use of a conduit
 
* The Cook t-Branch option has additional anatomic inclusion criteria that are specified below in section 4.0.3

Principal Investigator:	
[name]  University of Washington Medical Center  Assistant Professor of Vascular Surgery  University of Washington

Sub-investigator:	
[name]  Harborview Medical Center  Professor and Chief of Vascular Surgery  University of Washington

Data Safety Monitor(DSM)	[name] University of Washington Medical Center Assistant Professor of Anesthesiology and Pain Medicine University of Washington
Monitoring	Institute of Translational Health Services (ITHS)
Electronic Data Capture (Host)	University of Washington 
Core Lab	N/A

A list of all articles referenced in this protocol is contained in **Appendix I: References**.

## 1.0 STUDY GOAL AND OBJECTIVES

The goal of this study is to evaluate the performance of Branched Thoracic Endovascular Aneurysm Repair (B-TEVAR) with visceral vessel (i.e. celiac, superior mesenteric, inferior mesenteric, renal and anterior spinal artery) preservation in subjects with thoraco-abdominal aortic aneurysms. The specific objectives of the study are to:

1. Evaluate the safety of the branched thoracic endovascular grafts at 30 days, 6 and 12 months and annually for 5 years post-implant.
2. Evaluate the ability to deliver physician modified thoracic endovascular grafts within the peri-visceral aorta in order to preserve unimpeded blood flow into vital visceral vessels that arise from an aneurysm.
3. Evaluate the ability of physician modified thoracic endovascular grafts to exclude the thoraco-abdominal aortic aneurysm.

## 2.0 BACKGROUND AND RATIONALE

13,000 Americans die each year from rupture of an aneurysm in the aorta, which is the ninth leading cause of death in men over age 55. Aortic aneurysms are four times more common in men than in women and usually occur in those over age 50. Approximately one percent of men between the ages of 55 and 64 will have a significant aneurysm, and the likelihood increases to about four to six percent of those men over the age of 75.

Aortic aneurysms that involve the arteries to the intestines and kidneys are called thoraco-abdominal aortic aneurysms (TAAA) and are classified according to the Crawford classification system as modified by Safi. The risk factors for degenerative TAAA include tobacco use, hypertension, hyperlipidemia, male sex, and family history. Approximately 80% of TAAA are due to aortic atherosclerotic degeneration. An additional 20% develop TAAA as a consequence of aortic dissection with dilation of the false lumen.

Elective treatment of TAAA is done to prevent rupture. Without operation, about 25% of patients not deemed fit for surgery die within 1 year due to rupture. Traditional surgical therapy

involves an extensive incision extending from the chest to the abdomen. Cardiopulmonary bypass is often required. The operation carries significant risk of morbidity and mortality. Large population based studies have found a 20% peri-operative mortality which rises to 30% at 1 year.

Endovascular therapy has been developed to treat aneurysms involving the thoracic and abdominal aorta. Endovascular stent grafts have significantly reduced the peri-operative risk of surgery. Given the morbidity associated with open operation for TAAA, there is great optimism that endovascular therapy may significantly reduce the peri-operative risk of TAAA repair as well. Because TAAA involve the vital visceral blood vessels to the intestines and kidneys, an endovascular treatment must preserve flow to these branches while excluding flow from the aneurysm. Currently, there are no commercial endografts available to treat aneurysms involving the peri-visceral aorta.

Physician modification of commercial stent grafts to create a branched endograft has been used to treat aneurysms involving the juxta-renal and peri-visceral aorta in several centers around in the United States. We seek to evaluate the safety and effectiveness of B-TEVAR using a physician modified FDA-approved, off-the-shelf device in order to treat TAAA. It is our hypothesis that such endovascular therapy is effective and has reduced risk of peri-operative complications compared to open surgical repair.

## **2.1 Treatment of Thoraco-abdominal Aortic Aneurysm**

The current (standard) treatments for thoraco-abdominal aortic aneurysms include observation alone ("watchful waiting"), open surgical repair of the aorta using a fabric substitute or "hybrid" visceral debranching with aortic stent graft placement. B-TEVAR is not currently considered conventional treatment in the United States.

### **2.1.1 Observation**

If an aortic aneurysm is small and not causing symptoms, the treating physician may perform an ultrasound, a CT or MRI scan every 6 to 12 months to assess changes in the size or shape of the aneurysm. Along with serial radiographic measurement, optimal medical therapy is instituted. This includes smoking cessation, blood pressure control, and administration of aspirin and a statin (cholesterol lowering medication that may slow the rate of aneurysm growth). Observation is usually used for aneurysms that are smaller than 5-6 cm in diameter, fusiform in shape, and those that are growing slowly,  $\leq 10\%$  per year. If the TAAA is large, irregular in shape, rapidly expanding, or is causing symptoms, it will require prompt treatment to prevent death due to rupture of the aneurysm.

Most patients with TAAA also have advanced medical co-morbid illnesses. In one large study, 40% of patients with TAAA referred to the major aortic center in Scotland were deemed unfit for open repair due to the severity of their medical illnesses. This number is likely an underestimate, as the most medically ill were not referred. Fifty-five percent of untreated patients had died by a median of 12 month follow up, half due to rupture.

### **2.1.2 Open Surgical Repair**

Open surgical repair has long been the standard treatment for *good risk* patients harboring thoraco-abdominal aortic aneurysms. Centers of excellence have reported the best outcomes with an estimated 5-8% peri-operative mortality among such good risk patients. One review of outcome data after more than 7,000 open TAAA repairs reported a 10% peri-operative mortality. These results are those achieved by centers of excellence among patients deemed to be satisfactory candidates for major open operation. They exclude the outcomes of those patients whose medical co-morbidities preclude open aortic replacement. In larger, population based datasets, the estimated peri-operative mortality exceeds 20% and rises to 30% at 1 year. These data reflect the “real world” experience with open surgery for TAAA, and indicate both a need to better risk stratify patients pre-operatively and to regionalize treatment to specialized centers focused on the care of these patients.

### **2.1.3 Hybrid Repair with Surgical Debranching**

“Hybrid” endovascular repair involves the creation of surgical bypasses from the iliac artery to the visceral arteries along with placement of an aortic stent graft to exclude flow to the aneurysm. This off-label technique was developed to mitigate the major physiologic stress of cardiopulmonary bypass, thoracotomy and proximal aortic cross-clamping that is required for open repair of TAAA. This approach has gained favor with some surgeons as it can readily be performed using commercially available stent grafts. Unfortunately, although aortic cross-clamping is avoided, the operation still confers the substantial risks of a major open vascular operation. The outcomes after hybrid repair vary widely, as some centers have used the technique for good risk patients and case series are enriched by lower extent TAAA (i.e. Crawford extent IV). Among good risk patients, mortality rates as low as 4% have been reported. When applied specifically to patients with TAAA who were not candidates for open repair, the outcomes are worse, with a 22% peri-operative mortality in one large series from a center of excellence. Pooling data from multiple case series, the peri-operative mortality rate is estimated to be around 15%. The hybrid approach is optimal for patients at increased risk from open repair whose anatomy is not amendable to branched endovascular repair, such as patients with aortic dissection involving the visceral vessels.

### **2.1.4 Branched Endovascular Stent Graft Repair**

There are several studies describing endovascular technologies for preserving vital aortic branch vessels during the course of endovascular repair of TAAA. Three treatment options have been reported. The first two utilize commercially manufactured stent grafts by Cook Medical. This includes a custom modified device (CMD) and the t-Branch standardized device. These devices are not FDA approved and are only in use under Physician Sponsored IDE studies in the USA. They are approved for use in Europe and are currently available for use there. The alternative option is physician modification of a commercial endograft to create reinforced fenestrations. This study currently utilizes physician modified endografts, and the purpose of this supplement is to add the commercial manufactured grafts as options for subjects in this study.

The largest in-human experience currently available for endovascular treatment of TAAA comes from two centers in the USA that have used a combination of a CMD and the standardized t-Branch option manufactured by Cook Medical. The CMD devices are customized to the patient's anatomy and require 6-12 weeks for manufacture in Australia prior to implantation. The t-Branch option is a single design that utilizes 4 down-going cuffs to allow for intra-operative flexibility in treating variable branch anatomy. Initial results from these centers have been very encouraging, and important lessons have been learned.

[name] at the University of California San Francisco has reported on his initial 50 patients treated with the Zenith t-Branch device. All patients were considered to be at elevated risk for open repair. His group recently published a subsequent report of 81 patients, some of whom were included in the initial reports. In these reports, he has demonstrated excellent effectiveness and safety, with 100% implant success, 4% peri-operative mortality, and 6% overall aneurysm related mortality. Among the first 22 patients, there was a 41% incidence of major morbidity. All patients suffered from “some combination of fever, leukocytosis, anorexia, malaise, thrombocytopenia and coagulopathy.” The most recent series reports a 3.7% incidence of permanent paralysis and a 20% incidence of temporary spinal cord injury, all of which occurred in the peri-operative period. These data demonstrate that the operation can be done safely in very sick patients, but that medical complications are common and are to be expected. In this report, there was a high incidence of re-intervention at 40%. Most of these reinterventions were performed endovascularly or were minor surgical procedures at access site and were well tolerated by the patients. Overall, 90% of the patients were “treated without procedure-related death, dialysis, paralysis, aneurysm rupture, or conversion to open repair.”

[name] has reported on 189 patients undergoing elective repair of TAAA using a variant of the Cook branched device. In this large series, there was 100% implant success and no intra-operative deaths. Post-operative mortality rates were 6.3% and 18.5% at 30 days and 1 year, respectively. Permanent spinal cord injury occurred in 7.1%. These data are remarkably similar to those achieved by [name] and his group at the University of California San Francisco. The Cleveland Clinic group is a high volume center of excellence for both open and endovascular TAAA repair. As such, patients had access to highly experience providers for either treatment modality. Among the 428 patients seen with TAAA in this study, 44% were deemed to be best treated with endovascular repair, again reflecting the prevalence of advanced medical co-morbidities in patients with TAAA. In a subsequent report with over 9 years of follow up, they report excellent branch stent performance. Incidence of re-intervention was 4-6% after a mean of 3 years follow up, and only 3 of 650 patients (0.4%) died due to branch stent complications. These data demonstrate that once successfully treated, the device can provide durable effectiveness.

The outcomes reported by two large European centers of excellence are similar to those from UCSF and the Cleveland clinic. [name] in Lille, France, reported the outcomes

of 89 patients treated on an elective basis with the Cook Custom Thoracic Branched Device. Thirty day mortality was 9%, spinal cord injury was seen in 8%, and 1 year survival was 87%. [name] in Malmo, Sweden, published the results of 72 patients, including 21 patients treated on an acute/emergent basis. These patients were treated with variants of the Cook Custom Thoracic Branched Device and the t-Branch design. Thirty day mortality was 7%, temporary spinal cord injury was seen in 31%, but this improved in a majority of patients. The most recent group of patients had a 13% incidence of permanent spinal cord injury. Adverse outcomes were highest among the patients treated for rupture, with mortality for elective, symptomatic, and ruptured patients of 4%, 7%, and 29%, respectively. These studies show that the endovascular treatment of TAAA is feasible, although the procedure remains a high risk undertaking.

The Cook CMD and t-Branch devices have performed admirably in patients with TAAA, particularly as these results have been achieved amongst patients deemed to be unfit for or at high risk of open repair. There are, however, some patients who cannot be treated with a custom device. As a custom device takes 6-8 weeks to manufacture, a subset of patients with large or symptomatic aneurysms cannot tolerate that delay and require a more rapidly available option. There are two such options, the Cook t-Branch device, which is a variant of the custom device, and a physician modified device. It is estimated that 10-15% of patients with TAAA will not be eligible for repair using the t-Branch device. This is due to anatomic constraints of the device. The t-Branch device utilized cuffs which are axially oriented. This design requires sufficient working room within the aneurysm sac around the stent graft. In some cases, the ability to use reinforced fenestrations is preferable as there is a high degree of flexibility in fenestration location and they do not require much space within the aneurysm sac. Furthermore, the t-Branch device is designed to treat 4 branches, so patients with more branches are ineligible, as are some patients with a Type 1 TAAA that may not require coverage of the renal vessels.

The addition of the Cook Low Profile devices- t-Branch and Custom Modified (CMD) would provide additional benefits. The Cook Low Profile devices use an 18F delivery sheath. The standard t-Branch device uses a 24F sheath. This size difference is clinically significant, as a significant number of patients, particularly women, have smaller iliac arteries than will accommodate a 24F sheath. Reduction of the sheath diameter is expected to dramatically increase the number of patients eligible for endovascular repair of their aneurysms. The smaller delivery sheath both improves eligibility of patients for the study and reduces the likelihood of access site injury or need for an ilio-femoral surgical conduit operation. This is best demonstrated in the report from the University of California San Francisco comparing the two device constructs used in their IDE study. Within our current IDE study, we have had several screen failures due to small caliber iliac access. This modification falls within the existing IDE study as it adds a newer generation of the commercially manufactured branched and fenestrated-branched endografts that are

currently in use in the study. The device materials are currently used in an FDA approved commercially available thoracic endograft.

Concurrent with the PS-IDE studies assessing the Cook Medical commercial devices, some surgeons have sought to individually modify existing stent grafts to create a customized fenestrated device. The design of the Zenith® TX2® endovascular graft (Cook: Bloomington, IN) lends itself to device modification. The graft can be unsheathed under sterile conditions on a back table and precise measurements can be used to create an appropriate series of reinforced fenestrations and/or cuffs that correspond to the patient's branch vessel anatomy (Figure 1). Gold or platinum markers are hand sewn into place along with PTFE graft or stent grafts to create reinforced fenestrations or short cuffs for anchoring and sealing covered stents into the branch vessels.

Along with the creation of fenestrations and cuffs, sutures can be used to tailor the graft diameter to the patient's unique anatomy. This modification facilitates precise alignment of the fenestrations in each unique patient's anatomy. (Figure 2) The device is then re-sheathed and implanted into the patient similar to a standard endovascular repair. Subsequently, wires and catheters are used to cross through the fenestrations and cuffs into the target arteries. Over these wires, stent grafts are deployed and sealed into the main modified endograft, creating sealed branches. (Figures 3 and 4)

Several centers have conducted these operations in an effort to fulfill the urgent clinical need for TAAA repair among patients at high risk for open repair. [name] at Dartmouth Hitchcock Medical Center presented his personal experience with 85 physician modified branched endovascular aneurysm repairs among patients deemed to be at high risk of open repair. Sixty-three of these cases were TAAA treated according to the protocol described here as B-TEVAR, using physician modification of the Zenith® TX2® with reinforced fenestrations/cuffs. The Zenith® TX2® thoracic device was used in conjunction with the Zenith® Flex® device as well as with the AFX™ device for distal seal and fixation. One additional patient was treated using a chimney. Among these 64 patients treated for TAAA, there were 4 peri-operative deaths (6.25%) and 2 patients with permanent spinal cord injury (3%). Of 245 successfully completed branches, there were no occlusions and 3 Type 3 endoleaks requiring percutaneous re-intervention. This study demonstrates an exceptional level of safety and effectiveness among this very high risk patient cohort.

[name] studied under [name] and assisted with 15 of the reported B-TEVAR procedures. The technique described here is based on this clinical experience. The component parts described in this IDE application are those utilized in the performance of these repairs. Specifically, proximal aortic stent grafts consisted of the Zenith® TX2® platform. In cases where the distal aorta was not aneurysmal, the TX2® would be used to

seal, even if this required utilization of permanent diameter reducing ties. In cases where there was no suitable infra-renal aorta for seal, then an Endologix AFX™ device or Zenith® Flex® device would be deployed to seal in the common iliac arteries. In patients who had undergone prior endovascular therapy for aortic or visceral artery disease, the same devices would be used and oversized appropriately for the existing aortic stent grafts, even if they were manufactured by a different company. As described above, one of the critical advantages of B-TEVAR over the T-branch design is that it can be highly adaptable to atypical anatomy. Such anatomy is often found in patients with TAAA.

To construct the reinforced fenestrations and branches, the radio-opaque Boston Scientific fibered coil or the tip of a Cope wire was used as a marking metallic ring. A similar procedure has been done using the Amplatz snare, as is done by [name] in his PMEG IDE trial. The function of these different options seems equivalent based on clinical experience. Selection of these different devices is a function of radiographic visualization, cost and ease of re-packaging the material. The loop snare has excellent radio-opacity. However, at 0.053 in diameter it is substantially bulkier than the coil or wire tip, which measures 0.018 in. In the case of multiple fenestrations that are at the same cranio-caudal level, for example, the added bulk of the larger snare in conjunction with the PTFE cuffs, may make re-constraining the device more difficult. Conversely, in a large patient where visualization may be more challenging and re-packaging is not anticipated to be difficult, the loop snare would be advantageous to provide improved radio-lucency and visualization. As such, different component parts are needed in different cases, as the physician must assess the competing interests of visualization, ease of repackaging, and cost.

The fenestrations are reinforced with Atrium PTFE which provides bulk to increase the seal zone for the branch as well as strengthens the fenestration. In B-TEVAR, the branch stents must seal into the fenestration, as Type III leaks would perfuse the TAAA. In [name] experience, this composite device of the Zenith® TX2® with a heat-sealed fenestration, reinforced with a radio-opaque metallic marker (tip of a Cope wire or Boston Scientific coil) and Atrium PTFE has been used for >200 branches without evident material failure. Three type III endoleaks were successfully treated with percutaneous re-intervention as reported by [name]. This technique then utilizes balloon expandable iCast stent grafts that are deployed across these fenestrations and proximally flared by overdilation to increase the contact between the branch stent and the Zenith® TX2® device. Self-expanding stents are used within the balloon expandable stent graft in selected cases to increase outward radial force, smooth the transition from the stiff iCast stent to a tortuous target artery, or correct a target vessel dissection or kink caused by the branch stent.

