### **8.15 Deaths**

Any deaths that are device related must be reported to the FDA via an IDE supplement within 10 business days of knowledge of the event. Any deaths that are not device related are reported annually. The investigator is also required to adhere to the reviewing IRB requirements for reporting of deaths. In addition, patients with an implanted device who expire before completing the study should have the device explanted for evaluation by a pathologist if possible.

Aneurysm related death is defined as:

- any death occurring within 30 days of the B-TEVAR procedure, regardless of cause,
- death due to aneurysm rupture or
- within 30 days following any secondary procedure intended to treat the aneurysm.

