## 9.2 Secondary Endpoints

### 9.2.1 Safety

The following secondary safety endpoints will be evaluated at 30 days, 12 months and annually to 5 years:

- All-cause mortality
- TAAA Related Mortality
- Freedom from permanent spinal cord injury
- Major Adverse Events (MAE)
- TAAA rupture
- Surgical conversion

The CEC will meet annually to review all MAE. All deaths that occur in the study will be adjudicated by the CEC. TAAA related death is any death determined by the CEC to occur as a result of the initial procedure (first 30 days or prior to hospital discharge), TAAA rupture, conversion to open surgical repair, or due to secondary intervention after B-TEVAR.

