- Vascular injury including damage to blood vessels and surrounding tissues, vessel dissection, perforation, plaque dissection, collateral vessel occlusion, tissue loss, arterial fistula, limb loss, gangrenous disease, worsened or new onset claudication, edema
- Neurological complications, such as paralysis (temporary or permanent), paraplegia, monoplegia, paresis, spinal cord ischemia, hemiplegia, bowel or bladder incontinence
- Multi-system organ failure
- Embolic and thrombotic events such as deep vein thrombosis, thromboembolism, microembolism, thrombophlebitis, pulmonary embolism, air embolism
- Gastrointestinal events such as paralytic or adynamic ileus, obstruction, fistulas, and Intestinal ischemia due to visceral artery injury, branch failure, or embolization
- Impotence, erectile dysfunction
- Urinary events such as hematuria, urinary retention, and urinary tract infection
- Radiation injury, late malignancy
- Allergic reaction to x-ray dye such as flushing, nausea, vomiting, itching, hives
- Generalized inflammatory response that may be associated with elevated levels of systemic mediators of inflammation, elevated temperature
- General discomfort related to the procedure or tests, sore throat, pain
- Infection— systemic or localized, sepsis, endograft
- Device events such as endograft occlusion, migration, dislodgement, endoleak, failure to align the fenestrations with the visceral arteries and/or stent fracture
- Irreversible (permanent) tissue loss (for example loss of fingers, toes hands and/or feet)
- Potential whole body reaction (SIRS - Systemic Inflammatory Response) to the grafts that are placed causing an acute inflammatory (protective tissue response to injury or destruction of tissues) response that is seen by an increased heart rate, increased breathing rate, a white blood count that is either increased or decreased, increased or decreased body temperature. These conditions may lead to organ failure such as kidney failure potentially requiring the need for dialysis, respiratory failure potentially requiring the need to be on a ventilator (breathing machine), anemia potentially requiring the need for transfusions

- Branch vessel occlusion
- Aneurysm rupture
- Conversion to open surgical repair
- Death

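### Both definitions of aneurysm-related death omit late deaths from graft or branch failure that occur without rupture, conversion or re-intervention, so this secondary endpoint can err only downward

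*Protocol*

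**What the plan says.** The Protocol Summary lists "Aneurysm related mortality" as a secondary safety endpoint at 30 days, 12 months and annually to 5 years. Section 9.2.1 lists the same endpoint under the name TAAA-related mortality, at the same times.

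The term is defined twice.

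- **Section 8.15 (Deaths)** has three limbs: "any death occurring within 30 days of the B-TEVAR procedure, regardless of cause"; "death due to aneurysm rupture or"; and death "within 30 days following any secondary procedure intended to treat the aneurysm".
- **Section 9.2.1 (Safety)** counts deaths that the Clinical Events Committee (CEC) finds to have occurred "as a result of the initial procedure (first 30 days or prior to hospital discharge), TAAA rupture, conversion to open surgical repair", or due to a secondary intervention after B-TEVAR. The same section sends every death in the study to the CEC.

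Three other places bear on the point. Section 2.1.4 supports durability with the statement that "only 3 of 650 patients (0.4%) died due to branch stent complications". Section 10.0 names "Intestinal ischemia due to visceral artery injury, branch failure, or embolization" among the risks of this type of device, together with renal stent occlusion, branch vessel occlusion and endograft infection. Section 8.15 also recognises device-related death, but only as a reporting category: "Any deaths that are device related must be reported to the FDA".

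**The concern.** A branched graft has a failure mode that a plain tube graft lacks: the aneurysm stays excluded while a branch to the bowel or kidney is lost. Take a subject who dies in month 8 of bowel infarction from an occluded superior mesenteric branch, or of graft infection, with no rupture, no conversion and no further procedure. Neither list has a limb for that death. A CEC that applies the lists as written would class it as unrelated to the aneurysm, even if it judged the device to be the cause.

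This is a rule the protocol states, not a detail left for later. Harmonising the two definitions with each other would not help, because both have the same gap. At stake is the mortality endpoint meant to separate aneurysm and treatment deaths from the heavy background mortality of these patients. The protocol also defines no mortality endpoint that matches the branch-death benchmark it quotes.

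**Working it through.** **1. What each definition counts**

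| Late death (after day 30 and after discharge) | 8.15 | 9.2.1 |
|---|---|---|
| Through aneurysm rupture | counted | counted |
| Due to open conversion | only within 30 days, and only if the conversion is a secondary procedure aimed at the aneurysm | counted |
| Due to another secondary intervention, such as on a branch | only within 30 days, and only if aimed at the aneurysm | counted |
| Branch occlusion, graft failure or infection, with none of the above | not counted | not counted |

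Only the last row is missed by both. Adding these deaths could only raise the endpoint, so the bias runs one way.

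**2. The protocol's own figure**

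3/650 = 0.46%. The stated 0.4% is this value truncated; rounded, it is 0.5%. The exact (Clopper-Pearson) 95% interval is 0.10% to 1.34%.

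**3. Expected number in this trial**

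Inputs: n = 60 (section 5.0) and p from step 2. Expected deaths = 60p. The chance of at least one = 1 − (1 − p)^60.

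| Rate p | Expected in 60 | Chance of at least one |
|---|---|---|
| 0.40% (as stated) | 0.24 | 21% |
| 0.46% (3/650) | 0.28 | 24% |
| 0.10% (lower limit) | 0.06 | 6% |
| 1.34% (upper limit) | 0.81 | 56% |

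At 3/650 the chance of two or more is 3%.

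**4. Scaling to 5 years (assumption)**

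Section 2.1.4 gives a mean follow-up of 3 years, but attaches it to re-intervention. I assume it also applies to the deaths and that the hazard is constant. The 5-year rate is then 1 − (1 − 0.0046154)^(5/3) = 0.77%.

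- Expected in 60: 60 × 0.00768 = 0.46.
- At least one: 1 − (1 − 0.0046154)^100 = 37%, since 60 × 5/3 = 100.
- Two or more: 8%.
- At the upper confidence limit, the scaled rate of 2.23% gives 1.34 expected and a 74% chance of at least one.

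**5. Effect of one death**

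1/60 = 1.7 percentage points. For scale, the 6% aneurysm-related mortality quoted from another series in section 2.1.4 would be 0.06 × 60 = 3.6 deaths.

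**6. Why steps 3 and 4 give ceilings at the assumed rate**

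They treat all 3 of the 650 deaths as ones the definitions would miss, although the protocol does not say how many were early or followed rupture or re-intervention. They also keep all 60 subjects at risk throughout, although section 6.1 (Step 4) allows that some staged subjects never receive the branched graft. In the other direction, they cover branch-stent deaths only; the protocol gives no rate for late graft-infection deaths.

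**The case against.** The strongest reply is that nothing is lost. The month-8 death in the example counts in all-cause mortality, a secondary endpoint at the same times. It also counts among major adverse events, where death and bowel ischemia are both listed. The CEC reviews it, and if device related it goes to the FDA. The endpoint is named for the aneurysm, and section 8.15 keeps device-related death as its own category, so the separation may be deliberate. This is a single-arm feasibility study of 60 patients, and no decision rule in the protocol depends on this endpoint.

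Much of that stands, and it keeps the point small. It does not close the gap. All-cause mortality is not specific to the device: at the 18.5% one-year mortality cited in section 2.1.4, about 0.185 × 60 = 11 subjects would die in the first year, and one branch death would not stand out. FDA reporting is not an endpoint. If the separation is intended, the protocol does not say so, and it provides no endpoint line for the deaths set aside.

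Two stronger readings are tempting, and the document supports neither.

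- A reader might infer that all late deaths from graft or branch failure are excluded. They are not. Those through rupture count in both definitions, and those due to conversion or secondary intervention count in 9.2.1.
- A reader might infer that the reported mortality will be understated by a large share. Against 3.6 counted deaths, one missed death would be 1/(3.6 + 1) = 22% of the total and two would be 2/(3.6 + 2) = 36%. Both figures are conditional on those deaths occurring, and two or more has a probability of only 3%, or 8% scaled to 5 years. The 6% behind the 3.6 also comes from another series, whose definition of aneurysm-related death the protocol does not give.

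**Conclusion.** The gap is real and narrow. As written, both definitions class as unrelated a late death from graft or branch failure, occlusion or infection that involved no rupture, conversion or secondary intervention. The endpoint can therefore be too low for this reason and never too high; it is not shown that it will be too low.

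At the protocol's own rate, at most about 0.28 such branch-stent deaths are expected in 60 subjects, or 0.46 by 5 years under constant hazard and an assumed 3-year mean follow-up. Zero is the most likely count at those point estimates. The confidence interval is wide because it rests on three deaths, and at its upper limit scaled to 5 years at least one is more likely than not. The severity is minor: a cheap improvement to a secondary endpoint, with no effect on either primary endpoint.

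**What to change.** Use a single definition in sections 8.15 and 9.2.1. The two now also differ on death before discharge, on open conversion, and on which secondary procedures count and for how long. Add one limb: death at any time that the CEC attributes to failure, occlusion, infection or erosion of the aortic graft or a branch stent. Apply it at 12 months and annually to 5 years.

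If the sponsor prefers to keep the endpoint confined to the aneurysm, the alternative is to say so and report these CEC-adjudicated device-related deaths as a separate line beside TAAA-related mortality at the same times.

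Either change takes about a sentence in each section and needs no new data, since the CEC already adjudicates every death. The cost of the added limb is that the reported TAAA-related mortality may be slightly less favourable.
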